15. IMMUNOGENICITY OUTCOMES

The primary analysis will be based on the PPS for analysis of immunogenicity. If, in any study intervention group, the percentage of vaccinated participants with serological results excluded from the PPS for analysis of immunogenicity is 5% or more, a second analysis based on the ES will be performed to complement the PPS analysis.

15.1. Primary Immunogenicity

15.1.1. Primary Immunogenicity Variables & Derivations

The primary immunogenicity endpoints are:

- OP Ab titers for each of the pneumococcal vaccine STs (3, 7F, 19A, 5, 1, 14, 8, 33F, 9V, 10A, 11A, 19F, 6B, 4, 18C, 6A, 12F, 22F, 15B, 23F) expressed as between groups GMT ratio, 1 month after the PCV20 dose (Day 31

for Co-Ad group and for Control group)

- RSV-A neutralizing Ab titers (ED60 and IU/mL) expressed as between groups GMT (ED60) ratio and GMC (IU/mL) ratio, 1 month after the RSVPreF3 OA investigational vaccine dose (Day 31 for Co-Ad group and Day 61 for Control group)
- RSV-B neutralizing Ab titers (ED60 and IU/mL) expressed as between groups GMT (ED60) ratio and GMC (IU/mL) ratio, 1 month after the RSVPreF3 OA investigational vaccine dose (Day 31 for Co-Ad group and Day 61 for Control group)

See 7.4 for details on the handling of multiple primary endpoints.

15.1.2. Intercurrent Event Handling and Data Imputation for Primary Immunogenicity Variables

Missing data will not be replaced.

15.1.3. Primary Analysis of Primary Immunogenicity Variables

The primary immunogenicity endpoints will be analyzed as follows:

- For between group assessment GMT/GMC ratio for PCV20 administered alone (Control group) over PCV20 co-administered (Co-Ad group) at 30 days after administration of PCV20 dose (Visit 2, Day 31) and 2-sided 95% CI will be produced for OP Ab titers for each of the pneumococcal vaccine STs, where 2-sided 95% CIs will be derived from an ANCOVA model on \log_{10} transformed titers and presented alongside descriptive GMTs/GMCs and 95% CIs. The ANCOVA model will include the intervention group and age category (age at vaccination: 60 to 69, 70 to 79, or ≥ 80 YOA) as fixed effects, and the pre-dose \log_{10} -transformed titer as covariate. Results will be graphically presented using forest plots
- Between groups GMT/GMC ratio for RSVPreF3 OA administered alone (Control group) over RSVPreF3 OA co-administered at 30 days after administration of RSVPreF3 OA dose (Visit 2 for Co-Ad group, Visit 3 for Control group) and 2-sided 95% CI will be produced for RSV-A neutralizing Ab titers (ED60 and IU/mL), where 2-sided 95% CIs will be derived from an ANCOVA model on \log_{10} transformed titers and presented alongside descriptive GMTs/GMCs and 95% CIs. The same ANCOVA model used for the PCV20 GMT ratio will be applied for this summary. Results will be graphically presented using forest plots.
- Between groups GMT/GMC ratio for RSVPreF3 OA administered alone (Control group) over RSVPreF3 OA co-administered at 30 days after administration of RSVPreF3 OA dose (Visit 2 for Co-Ad group, Visit 3 for Control

group) and 2-sided 95% CI will be produced for RSV-B neutralizing Ab titers (ED60 and IU/mL), where 2-sided 95% CIs will be derived from an ANCOVA model on \log_{10} transformed titers and presented alongside descriptive GMTs/GMCs and 95% CIs. The same ANCOVA model used for the PCV20 GMT ratio will be applied for this summary. Results will be graphically presented using forest plots.

Missing results will not be replaced.

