6.3.3 Intervention Allocation to the Participant

Approximately 1090 eligible participants will be randomly (1:1) assigned to 2 study groups using a centralized randomization system on internet at Visit 1 (Day 1). The randomization algorithm will use a minimization procedure accounting for age (60 to 69, 70 to 79 or ≥ 80 years) and center. Minimization factors will have equal weight in the minimization algorithm.

After obtaining the signed and dated Informed Consent Form (ICF) from the participant and if the participant eligible, the delegated clinical trial staff will access IWRS. Upon entering the participant ID and age, the randomization system will determine the treatment group and provide the treatment number to be used for the trial intervention. The treatment number(s) to be used for subsequent dose administration(s) will be provided by the same IWRS.

Instructions related to instances when IWRS is not available will be provided to the site.

Refer to the IWRS user manual for additional information related to the treatment number allocation.

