9.3.1 Primary Endpoint(s)/Estimand(s) Analysis

The primary endpoints are described in [Section 3.0](#). The confirmatory analyses of non-inferiority will be based on the PPS.

- Method for non-inferiority of the PCV20 in terms of opsonophagocytic (OP) Ab GMT between groups ratio for each of the pneumococcal vaccine serotypes at one month after the PCV20 dose (i.e., at Day 31 for both groups):
 - The 2-sided 95% CI for Group GMT ratio between the PCV20 administered alone (control group) over PCV20 (co-ad group) co--administered with the RSVPreF3 OA investigational vaccine will be derived from an analysis of covariance (ANCOVA) model* on \log_{10} transformed titer.
- Method for non-inferiority of RSV investigational vaccine in terms of RSV-A neutralizing antibody geometric mean titer (GMT) between groups ratio at one after the RSVPreF3 OA investigational vaccine dose (i.e., at Day 31 for the co-ad group and at Day 61 for the control group):
 - The 2-sided 95% CI for RSV-A neutralizing antibody GMT ratio between RSVPreF3 OA investigational vaccine administered alone (control group) over RSVPreF3 OA investigational vaccine when co-administered with the PCV20 vaccine (co-ad group) will be derived from an ANCOVA model* on \log_{10} transformed titer.
- Method for non-inferiority of RSV investigational vaccine in terms of RSV-B neutralizing antibody geometric mean titer (GMT) between groups ratio at one after the RSVPreF3 OA investigational vaccine dose (i.e., at Day 31 for the co-ad group and at Day 61 for the control group):
 - The 2-sided 95% CI for RSV-B neutralizing antibody GMT ratio between RSVPreF3 OA investigational vaccine administered alone (control group) over RSVPreF3 OA investigational vaccine when co-administered with the PCV20 vaccine (co-ad group) will be derived from an ANCOVA model* on \log_{10} transformed titer.

**The model will include the intervention/treatment group and age category (age at vaccination: 60 to 69, 70 to 79 or ≥ 80 years) as fixed effects, and the pre-dose log₁₀-transformed titer as covariate. Missing data will not be replaced. Titers below the assay cut-off will be replaced by half the assay cut-off; titers above the upper limit of quantification (ULOQ) will be replaced by the ULOQ.*

9.3.1.1 Success Criteria for Non-inferiority and Testing sequence:

1st Sequence:

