*Pass 2019 alpha=2.5%, Two-Sample T-Tests for Non-Inferiority Assuming Equal Variance and Equal mean, Power=100 the Type II error (Beta). The Global Type II error (Beta) has been adjusted using Bonferroni's method (Global Type II error=sum of the individual Type II errors).

For RSV: non-inferiority limit=0.176 (=log10[1.5]).

For each PCV vaccine strain: non-inferiority limit=0.301 (=log10[2.0]).

Reference Ratio=0.0212 (=log10[1.05])

Considering a slight interference of 1.05 in true GMTs in both groups with a common population standard error of 0.45 for the RSV-A and RSV-B neutralizing Ab and the respective SD's for each of the PCV serotype in log10

transformed concentration, the study has at least 93.7% power to meet the primary objectives.

For the same evaluable subjects of 490 subjects, a sensitivity power calculation was performed considering the interference of 1.1 and keeping the other assumptions as it is, a power of ~85% was observed.

[figure not shown]

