3. STUDY DESIGN

3.1. General Description

This is a phase III, open-label, randomized, controlled, multi-country study in healthy older adults of ≥ 60 YOA with two parallel groups. Participants will be randomly assigned to 2 study groups at Visit 1 (Day 1):

- Co-administration (Co-Ad) group: Study intervention administration of RSVPreF3 OA investigational vaccine and PCV20 vaccine co-administered on Visit 1 (Day 1)
- Control group: Study intervention administrations of PCV20 vaccine on Visit 1 (Day 1) and RSVPreF3 OA investigational vaccine on Visit 2 (Day 31).

Figure A: Study Schema

- AE=Adverse Event; Co-Ad group=Co-Administration group; D=Day; N=Number of participants; PCV=20-valent pneumococcal conjugate vaccine; pIMD=potential Immune-Mediated Disease; RSV=RSVPreF3 OA; SAE=Serious Adverse Event.
- Healthy older adults ≥ 60 YOA will be enrolled in this study according to the inclusion and exclusion criteria (see protocol Section 5.0). Approximately 1090 participants will be randomly assigned to the 2 study intervention groups in a 1:1 ratio prior to intervention to provide approximately 545 enrolled participants in each study intervention group.

The randomization algorithm will use a minimization procedure accounting for age (60-69, 70-79, or ≥ 80 years) and center. Minimization factors will have equal weight in the minimization algorithm. Participants will be enrolled in 3 age categories with a balance between males and females. It is intended to enroll:

- Approximately 40% of participants 60 to 69 YOA, approximately 30% of participants 70 to 79 YOA, and approximately 10% of participants ≥ 80 YOA. The remaining 20% will be distributed freely across the 3 age categories.
- Approximately 40% of participants from each sex. The remaining 20% can be distributed freely across the 2 sexes.

Table A: Study Groups

Study groups	Number of participants	Age (min)	Study interventions
Co-Ad	545	≥ 60 years	RSVPreF3 OA and PCV20 co-administered
Control	545	≥ 60 years	RSVPreF3 OA and PCV20 administered separately

The total duration of the study participation differs for the 2 study intervention groups:

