7. STATISTICAL CONSIDERATIONS

7.1. Adjustments for Covariates and Factors to be Included in Analyses

The following factors will be used in the ANCOVA analyses: age group at vaccination (60 to 69, 70 to 79 or \geq 80 YOA) and study intervention group (Co-Ad or Control). The following covariate will be used in the ANCOVA: pre-dose \log_{10} -transformed titer as covariate. For details, refer to 15.1 and 15.2.

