7.4. Multiple Comparisons / Multiplicity

There are 3 primary endpoints to be accounted for in this study. In order to eliminate the need to adjust alpha, testing for these endpoints will take the following sequence:

- 1st Sequence:
 - 1) The upper limit (UL) of the 2-sided 95% CI of the GMT ratio (control group divided by Co-Ad group) for each individual pneumococcal vaccine serotype as measured by OP Ab is ≤ 2 .
AND
 - 2) The UL of the 2 sided 95% CI of the GMT ratio (control group divided by Co-Ad group) between the control group versus Co-Ad group for RSV-A neutralizing antibody titer one month after the RSVPreF3 OA investigational vaccine dose is ≤ 1.5 .
- 2nd Sequence:
 - 3) The UL of the 2 sided 95% CI of the GMT ratio (control group divided by Co-Ad group) between the control group versus Co-Ad group for RSV-B neutralizing antibody titer one month after the RSVPreF3 OA investigational vaccine dose is ≤ 1.5 .

Testing will progress in the 2nd sequence only if the 1st sequence is a success.

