15.1.4. Sensitivity Analysis for Primary Immunogenicity Variables

All three primary immunogenicity endpoints analyses will be repeated again using a different ANCOVA model. The ANCOVA model will include the study intervention group and age category (age at vaccination: 60-69, 70-79 or ≥ 80 years) as fixed effects, center as the random effect and the pre-dose \log_{10} titer as regressors.

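### Center is balanced by the minimisation but left out of the confirmatory ANCOVA, so the primary non-inferiority intervals may be slightly wider than they need to be

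*SAP*

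**What the plan says.** - **Allocation.** SAP 3.1 states: "The randomization algorithm will use a minimization procedure accounting for age", and names center as the second factor. Protocol 6.3.3 adds: "Minimization factors will have equal weight in the minimization algorithm".
- **Confirmatory model.** Protocol 9.3.1: "The model will include the intervention/treatment group and age category", with the pre-dose log10 titer as covariate. SAP 15.1.3 repeats this ("The ANCOVA model will include the intervention group and age category") and applies the same model to RSV-A and RSV-B. SAP 7.1 lists age group and study group as the only factors, then: "The following covariate will be used in the ANCOVA: pre-dose" log10 titer. None of these sections includes center.
- **Sensitivity model.** SAP 15.1.4 repeats all three primary analyses with "center as the random effect".
- **Decision rule.** All 20 serotypes and RSV-A must pass before RSV-B is tested. SAP 7.4: "Testing will progress in the 2nd sequence only if the 1st sequence is a success".
- **Reason given.** SAP 7.2, on multicenter studies, does not say why center is left out of the primary model.

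**The concern.** Two factors of equal standing drive the allocation, and only one of them reaches the confirmatory model. When arms are balanced within center, differences between centers largely cancel from the group contrast, so its true sampling error falls. An ANCOVA without center leaves those differences in its residual variance and reports the larger standard error.

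Only the primary interval decides non-inferiority, so the 15.1.4 repeat cannot return the lost precision to that decision. At stake is a little power in a first step where 21 tests must all succeed and one failure also blocks RSV-B. The validity of a positive claim is not at stake.

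**Working it through.** **Inputs from the documents** (SAP 2.5, same as protocol 9.5; alpha from protocol 9.1)
- n = 490 evaluable per group; one-sided alpha 2.5%.
- Log10 SDs from 0.572 (serotype 3) to 1.096 (23F) for the 20 serotypes; 0.45 for RSV-A and RSV-B.
- Margins 2 (PCV) and 1.5 (RSV). True ratio 1.05, and 1.1 in the SAP's own sensitivity calculation.

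**Assumptions, not in the documents**
- c, the center share of the variance left after age and baseline: 0%, 2%, 5% or 10%.
- R², the share of variance explained by baseline and age: 0% or 20%.

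**Step 1: reproduce the plan's power.** Two-sample t-tests (noncentral t, 978 df), with type II errors summed as in the plan:
- Ratio 1.05: PCV 6.10% (stated ~6.2%) plus 2 × 0.03% for RSV (stated 0.04% each) gives 6.16%, so power is 93.8% (stated ~93.7%).
- Ratio 1.1: 14.3%, so power is 85.7%. SAP 2.5 says: "a power of ~85% was observed".
- The normal approximation used below gives 6.1% and 14.2%.

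**Step 2: effect of omitting center under exact balance**
- s0 = SD × √(1 − R²)
- True SE = s0 × √(1 − c) × √(2/490)
- Reported SE = s0 × √(2/490) without center; equal to the true SE with center
- Excess width = 1/√(1 − c) − 1
- Actual one-sided alpha without center = 1 − Φ(1.96/√(1 − c))
- Type II error = 1 − Φ[(log10 margin − log10 ratio − 1.96 × reported SE) / true SE]

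Example: 23F, ratio 1.05, R² = 0, c = 10%. Reported SE = 1.096 × √(2/490) = 0.0700; true SE = 0.0700 × √0.9 = 0.0664; log10(2/1.05) = 0.2798.
- Without center: (0.2798 − 1.96 × 0.0700)/0.0664 = 2.147, type II 1.59%.
- With center: 0.2798/0.0664 − 1.96 = 2.253, type II 1.21%.

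**Step 3: sum over 20 serotypes, RSV-A and RSV-B.** Type II error in %, without → with center, both at the same c:

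| | c = 2% | c = 5% | c = 10% |
|---|---|---|---|
| Excess interval width | 1.0% | 2.6% | 5.4% |
| Actual alpha without center | 2.4% | 2.2% | 1.9% |
| Ratio 1.05, R² = 0 | 5.7 → 5.4 | 5.2 → 4.5 | 4.3 → 3.2 |
| Ratio 1.05, R² = 20% | 1.35 → 1.27 | 1.18 → 1.01 | 0.94 → 0.67 |
| Ratio 1.1, R² = 0 | 13.4 → 12.8 | 12.3 → 10.8 | 10.6 → 8.0 |
| Ratio 1.1, R² = 20% | 3.7 → 3.5 | 3.3 → 2.9 | 2.7 → 2.0 |

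From unrounded values, the loss across the three shares is:
- Ratio 1.05: 0.3 to 1.1 points (R² = 0) or 0.1 to 0.3 points (R² = 20%).
- Ratio 1.1: 0.7 to 2.5 points (R² = 0) or 0.2 to 0.7 points (R² = 20%).

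For 23F, the most variable serotype, with R² = 20%, the half-width factor falls from 1.327 to 1.323, 1.317 or 1.308, against a margin of 2.

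**Step 4: minimisation instead of exact balance.** Simulation of 1090 participants minimised on three age groups and center (assumed 0.9 biased coin), with 20, 45 or 80 centers of unequal size and 10% not evaluable at random. Center variance was estimated by REML, and a zero estimate reverted to the model without center. There were 32,000 runs per cell, so the Monte Carlo standard error of alpha is √(0.025 × 0.975/32,000) = 0.087 points. Ranges are over the three numbers of centers:

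| c | SE ratio, without/with center | Alpha without center | Alpha with center |
|---|---|---|---|
| 0% | 1.001–1.002 | 2.43–2.65% | 2.43–2.68% |
| 2% | 1.009 | 2.37–2.47% | 2.48–2.58% |
| 5% | 1.023 | 2.17–2.32% | 2.39–2.54% |
| 10% | 1.049–1.050 | 2.01–2.13% | 2.50–2.60% |

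Real minimisation recovers slightly less than exact balance (4.9–5.0% excess width at c = 10%, not 5.4%), and the direction is the same. At c = 0 the two models hardly differ.

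**The case against.** The strongest reply is that nothing here contradicts the plan's own figures. Power was planned with unadjusted t-tests, so 93.7% never relied on center. In every scenario above the current model does at least as well as planned: at ratio 1.05 its summed type II error is 5.7% or less, against the stated ~6.28%. What is lost is extra power. The center-adjusted model is already prespecified as a sensitivity analysis, so readers will see both results. That is right, and it is why the point is minor. The sensitivity result still cannot change the decision.

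Second, the size rests on assumptions. The center share may be small: testing is run under the sponsor's laboratory, blinded to allocation, and pre-dose titer is already in the model. The largest losses need a 10% share with baseline and age explaining nothing. Summing type II errors also overstates the loss if endpoints are correlated: with an assumed common correlation of 0.6, the loss at ratio 1.05 and R² = 0 is about 0.8 rather than 1.1 points at a 10% share, and 0.2 points at 2%. All of this stands.

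Third, the change puts a model with narrower intervals into an open-label trial after SAP version 2.0, and a reversion rule could leave different tests on different models. This is a fair caution. It is met by making the change only before results by group are seen, and by the simulated alpha, which stayed at 2.4–2.7% with center in all 12 cells. At zero center share the model without center also reached 2.65%, so small differences in alpha should not be over-read. The objection that no degrees-of-freedom method is named also stands, and the fix should name one.

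**Conclusion.** The point holds and is minor. The confirmatory model omits a factor that the allocation balances, and any center variance left after age and baseline makes the primary intervals too wide. The direction is certain if such variance exists; the size is not, because the documents give neither the center variance nor the number of centers. For an assumed share of 2% to 10%, the intervals are about 1% to 5% too wide. The largest power loss, 2.5 points, needs a true ratio of 1.1, a 10% share and no variance explained by baseline and age. With 20% explained, no scenario loses more than 0.7 points. At a zero share there is no loss. The current analysis is valid and conservative; it gives up a little precision that the design has already provided.

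**What to change.** Before any results by group are seen:

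- Make the SAP 15.1.4 model (group and age category fixed, pre-dose log10 titer, center random) primary for all three primary endpoints, and keep the current ANCOVA as the sensitivity analysis.
- Prespecify that a center variance estimated at zero, or non-convergence, reverts that test to the current ANCOVA. Name the degrees-of-freedom method.
- Align protocol 9.3.1 and SAP 7.1, and record the change in SAP 3.3, which now declares none.

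If results by group have already been seen, leave the primary model unchanged. If the sponsor prefers to keep it in any case, SAP 7.2 should say why center is omitted.

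The cost is small, because both models are already written and no new data are needed. The price is a documented departure from the protocol model and the reversion rule. In the simulation that rule was used often only where it does no harm: the center variance was estimated at zero in 53–57% of trials at a 0% share, 5–9% at 2%, and 0.3% or less at 5% and 10%.

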15.1.4. Sensitivity Analysis for Primary Immunogenicity Variables

All three primary immunogenicity endpoints analyses will be repeated again using a different ANCOVA model. The ANCOVA model will include the study intervention group and age category (age at vaccination: 60-69, 70-79 or ≥ 80 years) as fixed effects, center as the random effect and the pre-dose \log_{10} titer as regressors.

15.2. Secondary Immunogenicity

15.2.1. Secondary Immunogenicity Variables & Derivations

The secondary immunogenicity endpoints are:

- Summary of participants with RSV-A neutralizing Ab titers (ED60 and IU/mL) expressed as GMT/GMC at pre-vaccination and at 1 month after the RSVPreF3 OA investigational vaccine dose (Day 31 for Co-Ad group, Day 61 for Control group) will be tabulated.
- Summary of participants with RSV-B neutralizing Ab titers (ED60 and IU/mL) expressed as GMT/GMC at pre-vaccination and at 1 month after the RSVPreF3 OA investigational vaccine dose (Day 31 for Co-Ad group, Day 61 for Control group) will be tabulated.
- MGI for within participants ratios of the post-dose GMT/GMC (at 1-month after the RSVPreF3 OA investigational vaccine dose) over the pre-dose titer (at baseline) for RSV-A neutralizing titers/concentrations will be tabulated.
- MGI for within participants ratios of the post-dose GMT/GMC (at 1-month after the RSVPreF3 OA investigational vaccine dose) over the pre-dose titer (at baseline) for RSV-B neutralizing titers/concentrations will be tabulated.
- Percentage of participants with PCV OP Ab titers for each serotype expressed as GMFR, ratio of OPA GMT at 1-month post-vaccination (Day 31 for Co-Ad group and Control group) over pre-vaccination will be tabulated. This is a within participant comparison.

- Percentage of participants with PCV OP Ab titers for each serotype expressed as participants with a 4-fold increase in OP Ab titers from pre-vaccination (Day 1 for Co-Ad group and Control group) to post-vaccination (Day 31 for Co-Ad group and Control group) will be tabulated.
- Percentage of participants with RSV-A neutralizing Ab titers (ED60 and IU/mL) expressed as GMT/GMC with a 4-fold increase in RSV-A neutralizing Ab titers from pre-vaccination (Day 1 for Co-Ad group and Control group) to 1 month post-vaccination (Day 31 for Co-Ad group, Day 61 for Control group) will be tabulated.
- Percentage of participants with RSV-B neutralizing Ab titers (ED60 and IU/mL) expressed as GMT/GMC with a 4-fold increase in RSV-B neutralizing Ab titers from pre-vaccination (Day 1 for Co-Ad group and Control group) to 1 month post-vaccination (Day 31 for Co-Ad group, Day 61 for Control group) will be tabulated.
- Percentage of participants with RSV-A neutralizing titers/concentrations equal to or above pre-defined assay cut-offs and their 2-sided 95% CIs will be tabulated.
- Percentage of participants with RSV-B neutralizing titers/concentrations equal to or above pre-defined assay cut-offs and their 2-sided 95% CIs will be tabulated.
- Percentages of participants with PCV OP Ab titers for each serotype expressed as those participants with OPA Ab titers \geq LLOQ (pre-defined assay cut-offs) at pre-vaccination and/or 1 month post-vaccination (Day 31 for Co-Ad group and Control group).

For the derivation of MGI and GMFR refer to 6.6.

